## APPENDIX II: FORMULAS USED FOR VISUAL ACUITY, REFRACTION AND CONTRAST SENSITIVITY DATA

Postoperative distance and intermediate visual acuity testing will be performed using the M&S Technologies CTS-1000 Smart System© computerized vision testing system (M&S system). Postoperative near visual acuity testing will be performed using the Good-Lite self-calibrating, retro-illuminated box with 100% contrast ETDRS near charts at a test distance of 40 cm.

Key : “ \* ” = multiplication, “ - ” = subtraction, “ / ” = division, “ \*\* ” = exponent, log10 = log in base 10, CRF = Case Report Form

### Formulas for Converting Distance and Intermediate VA to LogMAR Values (M&S System):

LogMAR value = (85-letter score)/50

Example: A subject has distance letter score of 78  
Converting to LogMAR:  $(85-78)/50 = 0.14$  LogMAR

If the standard distance is not used for M&S system, no calculation adjustment will be needed since the M&S system already takes that into account.

### Formulas for Converting Near VA to LogMAR Values (ETDRS chart):

LogMAR value = (70-letter score)/50

If the standard distance for the chart was not used then the following formulas are used:

For near VA not tested at 40cm:

$\text{LogMAR} = \text{LogMAR}(\text{from formulas above}) + (\log_{10}(40) - \log_{10}(\text{test distance in cm}))$

Example: A subject has a near letter score of 65 and a test distance of 33 cm.

Converting to LogMAR:  $(70 - 65)/50 = 0.10$  LogMAR

Adjusting for test distance=  $0.1 + (\log_{10}(40) - \log_{10}(33)) = 0.10 + 0.083 = 0.183$

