## **20.5 VISUAL ACUITY CONVENTIONS AND GENERAL STATISTICS**

Visual acuity data will be converted to LogMAR values prior to analysis and adjusted for the test distance used if it is not the standard distance for the chart. Descriptive statistics will typically include sample size (N), mean, standard deviation (SD), median, minimum (Min) and maximum (Max) as appropriate for continuous variables. For continuous variables, statistical tests (e.g., t-test) assuming normality will generally be used. For categorical data, the frequency and proportion will be reported and Fisher's exact test or Chi-square test will generally be applied. For ordinal categorical data, the frequency and proportion will be reported with the Wilcoxon Rank-Sum test generally used.

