## APPENDIX D REFRACTION ADJUSTMENTS

Postoperative study manifest refractions are to be performed using the M&S System at a distance of 4.0 meters. Because 4.0 meters is not optical infinity, refraction adjustments are necessary to ensure proper vision testing that accounts for differences between the test distance and refraction distance. The adjustment required (in diopters) is 1/test distance (in meters). To adjust a 4.0-meter refraction to optical infinity, -0.25 D is to be added to the sphere of the refraction to obtain a true distance (infinity) correction. On the other hand, to adjust optical infinity to a 4.0-meter test distance, +0.25 D is to be given. In the case where the refraction distance (4.0 meters) and the vision test distance (4.0 meters) are the same, no adjustment is necessary. The following table lists the refraction adjustments required for the various vision tests in this study:

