## APPENDIX G INSTRUCTIONS FOR INTERMEDIATE VISUAL ACUITY TESTING

Intermediate visual acuity will be measured using the M&S System at a test distance of 66 cm using trial frames. Subjects should be reminded prior to testing that squinting is not allowed and the testing technician should carefully observe to ensure the subject is not squinting. If squinting is observed, the subject is to be reminded by the testing technician not to squint.

The M&S System will be set up to perform the required intermediate visual acuity tests in a specific order, with prompts on the screen to allow the technician to set up the subject for monocular or binocular testing, refraction adjustment as needed, and uncorrected or distance-corrected testing.

Intermediate visual acuity measurements are to be performed per the visit schedule in **Appendix A**. To test subjects monocularly, occlude the second eye with an occluder in the trial frame.

Visual acuity measurements are based on the total number of correctly read letters. Subjects should be persuaded to read the smallest letters possible even if they have to guess. Follow the testing process listed in **Appendix E**. At the end of the test, the number of letters correctly read will be displayed on the laptop screen, along with the LogMAR value and Snellen acuity. Record the total number of letters read in the EDC system.

**BEST-CORRECTED INTERMEDIATE LOW CONTRAST VISUAL ACUITY TESTING WITH ADD (BCIVA):** First eye monocular best-corrected intermediate visual acuity (10% contrast) with minimum add will be performed to determine the minimum amount of add necessary to achieve an intermediate visual acuity similar to the best-corrected distance visual acuity. BCIVA is to be tested at 66 cm under photopic conditions using the M&S System at 6 months. With distance correction in place, slowly build the amount of add necessary for the subject to achieve their best monocular intermediate visual acuity in the primary eye. In order to ensure the appropriate amount of add, at least one of the criteria below must be achieved:

- BCIVA similar to the subject's BCDVA. Document the amount of add necessary to achieve a BCIVA that matches the subject's BCDVA in the first eye. For example, if the subject's BCDVA is 20/20, the minimum ADD power will be the amount of add necessary to achieve a BCIVA of 20/20 at 66 cm. When the subject reaches a BCIVA that matches the BCDVA, record the minimum add power and BCIVA (# of letters correct).

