## APPENDIX H INSTRUCTIONS FOR NEAR VISUAL ACUITY TESTING

Near visual acuity will be measured using trial frames and Good-Lite 100% ETDRS near charts designed for 40 cm and the Good-Lite self-illuminated and self-calibrated illumination box. The Good-Lite illumination box is self-illuminated and self-calibrates to a light level of approximately 85 cd/m^2 (range of 80–110 cd/m^2 is acceptable). Room lighting is to be set at a level lower than the illumination from the light box, per manufacturer instructions. Ambient luminance should be from dim to dark to maximize pupil size. No surface (including reflective surfaces) within the subject's field of vision should exceed the chart background in luminance.

The light box should be placed at a test distance of 40 cm from the subject for testing near visual acuities. Subjects should be reminded prior to testing that squinting is not allowed and the testing technician should carefully observe. If squinting is observed, the subject is to be reminded by the testing technician not to squint.

To avoid chart memorization, charts will be changed between every visual acuity measurement. Monocular and binocular uncorrected testing will be completed before monocular distance-corrected testing is done.

Near visual acuity testing is to be performed per **Appendix A**. Visual acuity measurements are based on the total number of correctly read letters. Subjects should be persuaded to read the smallest letters possible even if they have to guess. Record the total number of letters read correctly for each near test on the case report form. Near score grids are to be used and must be retained as source documentation. A reference chart for the conversion of the number of correctly-read ETDRS letters to a Snellen line equivalent is provided later in this section.

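### A near acuity not taken at 40 cm is corrected for letter size but not for focus demand, and is then analysed as DCNVA at 40 cm

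*SAP*

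**What the plan says.** DCNVA at 40 cm is the first secondary effectiveness endpoint (Protocol 20.2, SAP 5.2.1). Protocol Appendix H fixes the set-up: "The light box should be placed at a test distance of 40 cm from the subject for testing near visual acuities". Protocol 20.5 nevertheless expects some departures, since acuities are to be "adjusted for the test distance used if it is not the standard distance for the chart".

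SAP Appendix II supplies the near rule: "If the standard distance for the chart was not used then the following formulas are used". Under the line "For near VA not tested at 40cm" the formula is LogMAR plus log10(40) minus log10(test distance in cm). It is illustrated so: "Example: A subject has a near letter score of 65 and a test distance of 33 cm". The result is given as 0.183 LogMAR.

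For tests on the M&S system, a note shared by distance and intermediate acuity says "no calculation adjustment will be needed since the M&S system already takes that into account".

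Neither document limits how far from 40 cm a reading may be and still count. The mITT set is all randomized and implanted first eyes, and imputation applies only where 6-month data are unavailable (SAP 2.1). The clinical criterion, the ZHR00 median against 0.3 LogMAR, uses the safety population. The per-protocol set drops eyes with deviations that could affect the endpoints, as judged before lock, but test distance is not named.

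**The concern.** The distance is part of the endpoint's definition because it sets the focus demand at which the lenses are compared. Moving the chart changes two things: the angular size of the letters and the vergence reaching the eye. The formula handles the first only. Nothing else in the plan handles the second. The lens adjustment for DCNVA is a fixed -0.25 D, which takes the 4 m refraction to infinity and does not vary with where the near chart stands (Protocol Appendix D).

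An off-distance reading therefore counts as available data. It enters the mITT t-test and the safety-population median as though taken at 40 cm. Elsewhere the trial treats a focus change of this size as a separate measurement: defocus testing moves in 0.50 D steps, and 0.5 D of extra depth of focus is the success margin for the second primary endpoint.

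**Working it through.** **Inputs from the documents.** Endpoint distance 40 cm (Protocol Appendix H); size formula and 33 cm example (SAP Appendix II); defocus step 0.50 D (Protocol Appendix I); depth-of-focus margin 0.5 D (SAP 5.1.2); DCNVA power assumptions of a 1-line difference, SD 1.6 lines, 100 per group and one-sided alpha 0.025 (SAP 7.2).

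**Assumed, not in the documents.** The defocus slope of each lens near 40 cm, taken as linear, and the share of eyes tested off distance.

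**Step 1: the SAP's figure.** (70 - 65)/50 = 0.10. log10(40) - log10(33) = 0.0835. The sum is 0.1835, so the stated 0.183 reproduces apart from truncation. The sign is right: a closer chart subtends a larger angle, so LogMAR rises. The formula is correct as a visual-angle conversion.

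**Step 2: the focus demand.** Demand in D = 100/distance in cm. At 40 cm it is 2.50 D.

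| Chart at | Demand (D) | Difference from 40 cm (D) | Size term (LogMAR) |
|---|---|---|---|
| 33 cm | 3.03 | +0.53 | +0.084 |
| 36 cm | 2.78 | +0.28 | +0.046 |
| 38 cm | 2.63 | +0.13 | +0.022 |
| 45 cm | 2.22 | -0.28 | -0.051 |
| 50 cm | 2.00 | -0.50 | -0.097 |

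The third column is left uncorrected. In the SAP's example it exceeds both 0.5 D yardsticks. At 4 m the same omission is negligible: 1/3.5 - 1/4 = 0.04 D.

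**Step 3: error for one eye at 33 cm.** Error = slope x 0.53 D. At 0.05 LogMAR per D it is 0.03; at 0.40 LogMAR per D it is 0.21. The powered difference is 1 line, or 0.10 LogMAR.

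**Step 4: effect on the comparison.** Shift in the lens difference = share of eyes off distance x difference in slope between lenses x 0.53 D. With 10% of eyes at 33 cm in each arm and slopes differing by 0.2 LogMAR per D in either direction, the shift is 0.10 x 0.2 x 0.53 = 0.011 LogMAR, or 0.11 line. A true 1-line difference would then be estimated as 0.89 to 1.11 lines. Power, 0.993 under the SAP's assumptions, becomes 0.977 to 0.998. With no eye off distance the shift is zero.

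**Step 5: an example tolerance.** Allowing 0.10 D either side gives 100/2.60 = 38.5 cm to 100/2.40 = 41.7 cm.

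**The case against.** This is a contingency rule, and 33 cm merely illustrates its arithmetic. The protocol fixes 40 cm, the charts are designed for it, and a different distance is a procedural deviation that must be documented and monitored (Protocol 10.10). Nothing suggests that it will be frequent. Testers are masked and randomization lists are made per site, so off-distance testing should fall equally on both arms. A few eyes barely move a median. The per-protocol analysis can already drop such eyes.

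Most of this stands, and it limits the size of the problem. It does not close the gap. The per-protocol exclusion rests on unstated judgement, and the mITT and safety sets have no filter. Equal distribution between arms does not cancel the error if the lenses have different defocus slopes.

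A reader might go further and infer that DCIVA, the only primary endpoint with a hypothesis test, is affected in the same way. The documents do not support that. The M&S note covers distance and intermediate tests together, and its example is a distance score. The protocol describes resetting that system only where a room cannot give 4.0 m (Appendix F). For intermediate testing Appendix G is fixed: "Intermediate visual acuity will be measured using the M&S System at a test distance of 66 cm using trial frames". The note's wording is loose, but no off-distance DCIVA is provided for.

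A reader might also infer that testing too close flatters ZHR00 because its range is longer. Protocol Table 1 gives a range through 3.0 D and says nothing about the shape of the curve within it. The 33 cm example, at 3.03 D, lies just beyond that range. No slope is given for either lens.

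**Conclusion.** The concern holds for near acuity. The SAP states a rule that gives a value at the wrong focus demand for an endpoint defined by distance, and no named safeguard removes it from the mITT test or the safety-population median. The 0.53 D in the SAP's example is certain, because it follows from the distances alone. The per-eye error of about 0.03 to 0.21 LogMAR rests on assumed slopes of 0.05 to 0.40 LogMAR per D. The trial-level effect also depends on an assumed share of off-distance tests: it is small unless they are common and zero if there are none. The direction by lens is unknown, so a claim of bias toward ZHR00 would not be justified. No sample size, alpha or power figure in the plan needs to change. The point merits action because the correction is cheap and is better settled before the data are seen.

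**What to change.** Before database lock, amend SAP Appendix II and align Protocol 20.5 with it:

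- Set a distance tolerance for near tests and accept the size-adjusted value as a 40 cm value only within it. The limit is the sponsor's choice; 0.10 D (about 38.5 to 41.7 cm) is one example and has no source in the documents.
- Name near readings outside the tolerance as endpoint-relevant deviations, excluded from per-protocol.
- Beside the planned analyses, repeat the DCNVA mITT test with those readings set to missing and imputed by the planned method, and repeat the ZHR00 safety-population median with them left out. State whether they count toward the 10% missingness that triggers the tipping-point analysis.
- State that the M&S note on non-standard distance applies to 4 m tests, and that any DCIVA not taken at 66 cm is handled in the same way as an off-distance DCNVA.

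The cost is wording, one sensitivity analysis and possibly a few more missing values. The near formula already needs the actual distance. Confirm that it is captured for near and intermediate tests, because the explicit instruction to measure and record it appears only for distance testing (Protocol Appendix F).

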### Converting from LogMAR to Snellen and Decimal Equivalent:

Snellen denominator= $20 * (10^{**(\text{LogMAR value})})$

Decimal VA=  $20 / (\text{Snellen Denominator})$

Example: A subject has a LogMAR score of 0.20

The Snellen denominator is:  $20 * (10^{**(0.20)}) = 20 * (1.585) = 31.7 = 20/32$

Decimal VA =  $20/32 = 0.625$

## Formulas for Refractive Data

### **Converting to Plus Cylinder Notation:**

If the original cylinder value is positive then the following formulas are used:

1. New sphere value=original sphere value
2. Final cylinder value=absolute value of the original cylinder value
3. Final axis value=original axis value

If the original cylinder value is negative then the following formulas are used:

1. New sphere value=original sphere value + original cylinder value
2. Final cylinder value=absolute value of the original cylinder value
3. Final axis value: if original axis is  $>0$  and  $\leq 90$  then final axis=original axis +90; if the original axis  $>90$  and  $\leq 180$  then final axis=original axis – 90

**Adjusting for Infinity:** Final sphere=new sphere (in plus cylinder notation) – 0.25

### **Spherical Equivalent**

1. Spherical equivalent=final sphere + (0.5\*final cylinder)
2. Adjusted spherical equivalent=spherical equivalent – target spherical equivalent

### Examples:

Refraction: sphere: -0.25 cylinder: -0.50 axis: 80 with target SEQ=-0.13

In plus cylinder notation: sphere=-0.75, cylinder=0.50 axis=170

Adjusting for infinity: sphere=-1.00, cylinder=0.50 axis=170

Spherical equivalent=-1.00 + 0.5\*(0.50) = -0.75

Adjusted spherical equivalent= -0.75 – (-0.13) = -0.62

### Formulas for Converting Contrast Sensitivity to Log Units (M&S System):

Log units =  $\log_{10}(1/\% \text{ value from the CRF})$

For example: 50% contrast will be  $\log_{10}(1/0.5) = \log_{10}(2) = 0.3010$

### APPENDIX III: ALGORITHM FOR OVERALL SPECTACLE INDEPENDENCE

A composite dichotomous (0 or 1) Overall Spectacle Independence score classifies overall spectacle independence based on all of the Need (Questions 1a-1c), Wear (Questions 2a-d), and Strain (Questions 3a-d) items from PRSIQ. Answering all of Need items (Questions 1a-c) with "No" and all of the Wear (Questions 2a-d) and Strain (Questions 3a-d) items with "None of the time" results in a score of 1. Answering any of the Need items (Questions 1a-c) with "Yes," or any of the Wear (Questions 2a-d) or Strain (Questions 3a-d) items with "All of the time," "Most of the time," "Some of the time," or "A little of the time" results in a score of 0.

Overall Spectacle Independence is scored as follows:

- Overall Spectacle Independence is achieved (score=1)
  - For questions 1a-1c, participants indicate "No" to the Need for correction for distance, intermediate, and near vision; and
  - For question 2a-d, participants indicate "None of the time" to the Wear of correction for distance, intermediate, near vision, and overall vision; and
  - For question 3a-d, participants indicate "None of the time" to Strain to see when not wearing glasses for distance, intermediate, near, and overall vision.
- Overall Spectacle Independence is not achieved (score=0)
  - For questions 1a or 1b or 1c, participants indicate "Yes" to the Need for correction for distance, intermediate, and near vision; or
  - For question 2a or 2b or 2c or 2d, participants indicate "All of the time" or "Most of the time" or "Some of the time" or "A little of the time" to the Wear of correction for distance, intermediate, near vision, and overall vision; or
  - For question 3a or 3b or 3c or 3d, participants indicate "All of the time" or "Most of the time" or "Some of the time" or "A little of the time" to Strain to see when not wearing glasses for distance, intermediate, near, and overall vision.

Complete data is needed for each composite dichotomous score; no imputations for missing values should be used. Any individual missing response on at least one relevant item will be assigned as a missing value for overall spectacle independence variable.
